8.1.2.1 Survival Status

The survival status of the subject during primary hospitalization will be recorded from randomization up to the time of death, hospital discharge, or Day 30, whichever occurs first. The date and time of death / hospital discharge / Day 30 will be recorded, as applicable. The survival status check during primary hospitalization will be at 24 hours (the date and time of death / hospital discharge will be recorded, as applicable). If subject is discharged alive prior to 6 hours, then the subject will be followed up to assess 6-hour survival status, SAEs, and AESIs.

The primary cause of death, as determined by the investigator, will be recorded.

Discharge / transfer information will be recorded (eg, transferred to another hospital, transferred to skilled nursing facility, transferred to in-patient rehabilitation, discharged to home, or transitioned to comfort care / palliative care). If subject is discharged within 2 days of enrollment, discharge time will also be recorded. Additionally, if the subject is designated "do not resuscitate", the date and time (where applicable) will be recorded.

8.1.2.2 Surgical or Interventional Radiological Procedures Performed to Stop Bleeding Related to the Primary Injury, Through the First 24 Hours After Randomization

All surgical or interventional radiological procedures performed to stop bleeding related to the primary injury, through the first 24 hours after randomization, will be recorded.

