8.5.4 In-hospital Follow-up Period

Subjects will be followed up until death, discharge from hospital, or Day 30, whichever occurs first. If subject is discharged alive prior to 6 hours, then the subject will be followed up to assess 6-hour survival status, SAEs, and AESIs. Transfer to another healthcare facility will be considered as discharge from hospital. For details regarding Informed Consent, refer to [Section 12.3](#) and [Section 12.3.1](#).

The following assessments will be performed:

- IP accountability (to be performed in the IRT system when feasible within 24 hours after randomization)
- Demographics (to be recorded when feasible)*
- Medical history and Charlson Comorbidity Index (to be recorded when feasible)*

- Prior and concomitant medications (medications that impact bleeding and coagulation [including antiplatelets] for at least 1 week prior to randomization; tranexamic acid [if administered]; prohibited concomitant medications administered from trauma time through 6 hours after randomization; and anticoagulants, thrombolytic agents, and procoagulants used to treat AESIs; to be recorded when feasible)*
- Concomitant procedures (any surgical or interventional radiological procedures, or other life-saving interventions, used to treat an SAE or AESI at any time through the study will be recorded)*
- SAEs and AESIs
- Survival status (survival status of the subject during primary hospitalization will be recorded from randomization up to the time of death, hospital discharge, or Day 30, whichever occurs first. The date and time of death / hospital discharge / Day 30 will be recorded, as applicable. For expired subjects, details of their death may be recorded on the Subject Death Record. The survival status check during primary hospitalization will be at 24 hours [the date and time of death / hospital discharge will be recorded, as applicable]. If subject is discharged alive prior to 6 hours, then the subject will be followed up to assess 6-hour survival status, SAEs, and AESIs)*
- Blood product transfusions (eg, RBCs, FFP, whole blood, cryoprecipitate, intraoperative salvaged [cell-saver] blood, and platelets) and IV fluid administrations (crystalloids and / or colloids) before arrival at the hospital through the 24 hours after randomization*
- All surgical or interventional radiological procedures performed to stop bleeding related to the primary injury, through the first 24 hours after randomization*
- Mode of transport to the hospital*

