Additionally, the following parameters will be both summarized and inferential statistics will be provided for them:

- Number of ventilator-free days .
- Number of ICU-free days.
- Number of hospital-free days.

Hospital length of stay will be calculated directly as date of discharge/death/discontinuation – date of randomization + 1 day, as in this study time in the study is the same as time in the (primary) hospital. Hospital lengths stay larger than 30 days should not occur, but if they do, hospital length of stay will be set to 30 days instead.

Missing start and end dates for ventilation and ICU will be replaced with the start and end date of the in-hospital period respectively. End dates that are after the end date of the in-hospital period will also be replaced with the end date of the in-hospital period for this calculation.

As subjects should be followed up for 30 days, any end date later than study day 30 will be replaced with the date of study day 30. Episodes that start after study day 30 will be disregarded entirely.

If multiple episodes are recorded for ventilation or ICU stay, the duration for each episode will be calculated and summed up, except that for cases where the end date of one episode coincides with the start date of the next, in which case the episodes are combined before calculating the duration in order to avoid counting the same day twice.

The number of ICU-free days, ventilator-free days and hospital-free days is calculated as 30 days less the number of days in ICU, on ventilator and in hospital respectively for subjects who do not die and who did not withdraw from the study or decline to continue participation. For subjects who die, it will be set to zero instead.

Subjects who withdrew or declined to continue participation will not be included in the main analysis, but a supplemental worst-case analysis will be conducted. For this worst case analysis the number of free days for subjects who withdrew or declined to continue participation will be calculated as study duration – number of days in ICU/on ventilation/in hospital respectively. The number of free days for all other subjects will be the same as in the main analysis.

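### Ventilator-, ICU- and hospital-free days count all time after transfer to another facility as free, and the worst-case analysis does not cover transfers (minor; exploratory endpoints)

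*SAP*

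**What the plan says.** The score results from rules in two documents.

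- Protocol 8.5.4 ends follow-up at death, discharge or Day 30 and adds: "Transfer to another healthcare facility will be considered as discharge from hospital".
- SAP 10.3.3 fills a missing ventilator or ICU end date with the end of the in-hospital period. For late dates it says: "End dates that are after the end date of the in-hospital period will also be replaced with the end date of the in-hospital period".
- Hospital stay in SAP 10.3.3 runs from randomization to discharge, death or discontinuation, "as in this study time in the study is the same as time in the (primary) hospital".
- The number of ICU-free, ventilator-free and "hospital-free days is calculated as 30 days less the number of days in ICU, on ventilator and in hospital respectively". This applies "for subjects who do not die and who did not withdraw from the study or decline to continue participation". Transferred subjects are not excepted.
- On deaths: "For subjects who die, it will be set to zero instead".
- Withdrawn or declining subjects are left out of the main analysis. In a supplemental worst-case analysis they score study duration less days on support or in hospital. For everyone else: "The number of free days for all other subjects will be the same as in the main analysis".

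Protocol 8.1.2.1 records where the subject went. The listed examples include "transferred to another hospital, transferred to skilled nursing facility, transferred to in-patient rehabilitation", home, and comfort or palliative care. SAP 10.3.3 does not use this variable.

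SAP Table 1 limits ventilator-free and ICU-free days to the primary hospital stay but puts no such limit on hospital-free days.

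**The concern.** A free-days score is meant to rank patients by how soon they came off support or left hospital, with death at the bottom. Here, leaving the trial hospital for another one earns the same credit as recovery, because every unobserved day to Day 30 is assumed free. The SAP does not make that assumption for withdrawals in its worst-case analysis, so two subjects with the same observed course get different scores depending on why observation ended.

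The problem is plainest for hospital-free days: a subject lying in a second hospital is not free of hospital, and Table 1 does not confine that endpoint to the first one. At stake is the meaning of the three scores and of the means, intervals and exploratory Wilcoxon p-values reported for them.

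**Working it through.** The documents give no sample size, power or expected value for these endpoints, so there is no plan figure to reproduce. The check applies the SAP 10.3.3 rule to contrasting courses.

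**Inputs.** The 30-day starting value, truncation at the end of the in-hospital period, zero for recorded death and the worst-case formula come from SAP 10.3.3. Transfer as discharge comes from Protocol 8.5.4. For illustration, ventilation and ICU stay each form one episode starting on Day 1, counted in calendar days.

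**Formula for a survivor who stays in the study.** Ventilator- or ICU-free days = 30 − min(episode end, discharge or transfer day, 30). Hospital-free days = 30 − min(discharge or transfer day, 30).

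| Course | Ventilator- / ICU- / hospital-free days |
|---|---|
| Weaned, out of ICU and home on Day 5 | 30 − 5 = 25 / 25 / 25 |
| Transferred on Day 5, still ventilated in ICU | 30 − 5 = 25 / 25 / 25 |
| Same course, kept on support at the trial hospital to Day 30 | 30 − 30 = 0 / 0 / 0 |
| Died in the trial hospital | 0 / 0 / 0 |

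The first two rows stay equal at every day checked: 28 at Day 2, 20 at Day 10, 15 at Day 15 and 10 at Day 20. The order can also reverse. A subject transferred on a ventilator on Day 5 (25 ventilator-free days) outranks one weaned at the trial hospital on Day 10 (30 − 10 = 20).

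**Comparison with withdrawal.** A subject ventilated throughout who withdraws on Day 5 scores 5 − 5 = 0 ventilator-free days in the worst-case analysis. A subject transferred on Day 5 after the same course scores 25 in both analyses.

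**Effect on an arm mean.** If support had in truth continued to Day 30, each such subject is over-credited by 30 − T days, where T is the transfer day. The overstatement of the mean is then at most (share transferred on support) × (30 − T). It is smaller if some are weaned after transfer. The shares below are assumptions.

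| Share transferred on support | T = 5 | T = 10 | T = 20 |
|---|---|---|---|
| 1% | 0.25 | 0.2 | 0.1 |
| 2% | 0.5 | 0.4 | 0.2 |
| 5% | 1.25 | 1.0 | 0.5 |
| 10% | 2.5 | 2.0 | 1.0 |

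For hospital-free days the relevant share is everyone moved to another hospital, on support or not.

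**Deaths elsewhere.** Transfer ends follow-up, and SAP 8.2.3 assumes no death where none is recorded. A subject who dies after transfer would normally keep the credited days instead of scoring zero. If that subject was off support at transfer, the error lies outside the bound above.

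**The case against.** The case for leaving the rule alone has substance.

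- **Exploratory status.** The p-values are exploratory and SAP 10.4 makes no multiplicity adjustment for them. This stands, and it sets the severity.
- **Deliberate scope.** A large simple trial limits its data collection, and in-hospital mortality likewise carries status at discharge forward. This explains why nothing is observed after transfer. It does not explain subtracting from a fixed 30, which credits days after the primary stay to endpoints that Table 1 confines to that stay.
- **Existing safeguards.** Protocol 10.3.1.1 tabulates discharged or transferred subjects by arm. SAP 10.3.3 also summarises the raw ventilator, ICU and hospital days and lists the episode dates. So transfers are not invisible; what is missing is an analysis that scores them differently.
- **Recorded dates.** A site may enter the transfer date as the ventilator stop date, so an episode still open at transfer may look closed. This stands, and the remedy must allow for it.

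Three stronger readings are tempting.

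- A reader might infer that the Wilcoxon test has an inflated false-positive rate. That would need transfer practice to differ between arms with no treatment effect. Site staff are blinded and randomization is within site, so the documents give no mechanism for it. A between-arm distortion could arise if treatment changed survival to transfer or its timing, but its size is unknown.
- A reader might infer that transferred subjects are the sickest survivors. The documents do not say so, and the listed destinations include skilled nursing and rehabilitation.
- A reader might infer that the main analysis should count every in-patient destination as hospital to Day 30. A subject sent to rehabilitation on Day 12 would then fall from 18 hospital-free days to 0, the score given to deaths. That is a debatable trade-off, not a correction.

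**Conclusion.** The concern holds as a minor point. By its stated rules, SAP 10.3.3 gives a subject transferred on support the same three scores as one who recovered and went home that day: 25 rather than 0 for a Day 5 transfer whose support continues to Day 30. The worst-case analysis, which removes this credit for withdrawals, leaves it in place for transfers. The 25-versus-0 contrast rests only on the SAP's rules and the stated course.

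The effect on arm means cannot be determined, because no transfer rate is given; the tabulated 0.1 to 2.5 days rest on assumed shares and transfer days. With similar transfer practice in both arms, the main consequence is a distorted score rather than a biased comparison. The primary and gated secondary conclusions do not depend on it.

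**What to change.** In SAP 10.3.3:

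1. Extend the supplemental worst-case analysis to subjects whose recorded discharge location is another hospital. Count the days after transfer as in hospital. Count a ventilator or ICU episode that has no end date, or ends on the transfer date, as continuing to Day 30. The Day 5 transfer on support then scores 0 / 0 / 0, in line with the withdrawal.
2. State how skilled nursing and in-patient rehabilitation are classified for hospital-free days.
3. Tabulate transfers by arm, destination and ventilator/ICU status at transfer.
4. Keep the current calculation as the main analysis, labelled as crediting days after transfer as free.

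The cost is SAP wording and derivation code; discharge location and episode dates are already collected. The downside is that the added analysis is pessimistic for subjects weaned or discharged soon after transfer, and a ventilator stop on the transfer date may sometimes be a true extubation. That is acceptable in a worst-case analysis reported beside the main one.

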10.3.4 Tranexamic Acid

The amount of infused tranexamic acid measured in mg will be summarized descriptively in the same way as the blood products described in [Section 10.3.1](#).

10.4 Multiple Comparisons and Multiplicity

If the threshold of the primary endpoint is met, the efficacy-related secondary endpoints (endpoints for the secondary objectives 1 to 3) will be analyzed sequentially in the order of their respective subsections of [Section 10.2](#). A gated testing approach will be used to

account for multiplicity, where testing will proceed in a stepwise manner conditioned on observing a statistically significant result for each preceding endpoint. Significance will be determined in the same manner as for the primary endpoint, by checking if the posterior probability for a difference in favor of BE1116 exceeds 97.5%.

No adjustment for multiplicity will be performed when p-values are reported for subgroup analysis or exploratory endpoints.

10.5 Missing Data and Imputation

See [Section 8.1](#) on the handling of missing data. Other data will not be imputed.

10.6 Treatment Compliance

Treatment compliance will not be evaluated as only a single dose is given. Issues with the administration of the single dose will instead be included in the exposure summary described in Section 11.1.

11 Safety Analyses

All safety analysis will be based on the Safety Population.

11.1 Extent of Exposure

Exposure to the IP will be descriptively summarized by treatment group, using the following variables:

- Number and percentage of subjects at each dose level (2000 or 3000 IU).
- Infusion duration (min). The infusion duration will be calculated as end time – start time – duration of any interruptions.
- Infusion rate (mL/min), calculated as dose in mL/infusion duration. Dose in mL will be calculating using the conversion factor 1000 IU = 40 mL.
- Number and percentage of subjects with interrupted infusion, including break-down by reason.
- Number and percentage of subjects with stopped infusion due to AE. This will be the number of subjects who have an AE with action taken with study treatment entered as “Drug Withdrawn”.

- Number and percentage of subjects whose dose level would be different if measured weight instead of estimated weight has been used (overdose and underdose).

IP administrations will be listed.

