3.2 Dose and Dosing Regimen

Subjects will receive a single IV infusion of either BE1116 or placebo, in addition to the study site's standard resuscitation methods and protocol.

The dose of BE1116 will be either 2000 IU or 3000 IU, based on the estimated or measured weight of the subject documented on arrival at the hospital:

- Weight < 75 kg (< 165 lbs): 2000 IU
- Weight \geq 75 kg (\geq 165 lbs): 3000 IU

Details regarding dose administration are provided in [Section 5.1.3](#).

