5.1.1 Description of BE1116

Details of BE1116 are provided in Table 2.

The lyophilized powder of BE1116 will be provided in labeled, single-use, glass vials. The product is provided in a study co-packaged kit (IP study kit) containing 3 vials of BE1116 (or placebo), 3 vials of sterile water for injection, and 3 Mix2Vial™ devices. The lyophilized concentrate of BE1116 must be reconstituted with sterile water for injection.

The formulation of BE1116 to be used in this clinical study is unchanged from the commercial form and will be labeled as IP.

Dose administration information is included in [Section 5.1.3.1](#).

Table 2 Description of BE1116

Substance name	BE1116
Trade name	Kcentra® / Beriplex®
Active substance	Concentrate of human coagulation Factors II, VII, IX, and X (PCCs), Protein C, and Protein S
Excipients	Heparin, antithrombin III, human albumin, sodium chloride, sodium citrate, hydrogen chloride, sodium hydroxide
Dosage form	Powder for reconstitution (1000 IU/vial) Provided together with diluent (sterile water for injection)
Dose	
 2000 IU for subjects with body weight < 75 kg (< 165 lbs) (2 vials) 3000 IU for subjects with body weight ≥ 75 kg (≥ 165 lbs) (3 vials) (Weight may be estimated and / or measured.)
Dosing regimen	Single dose
Infusion volume	Based upon dose: 
 80 mL for 2000 IU (2 vials) 120 mL for 3000 IU (3 vials)
Mode of administration	Intravenous infusion ^a

IP = investigational product; PCC = prothrombin complex concentrate.

^a Further details regarding dose administration are provided in the Site IP Manual.

BE1116 will be manufactured by CSL in accordance with ICH Good Manufacturing Practice (GMP) guidelines and local regulatory requirements.

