5.1.3.2 Dosing Modification

A partial dose of IP may be administered (eg, if there is a product error or user error when reconstituting / administering the IP if the remainder of the IP is unaffected, when infusion needs to be stopped due to patient care issues, or if vial(s) are damaged).

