5.1.3.4 Overdose

Overdose of BE1116 is defined as the infusion of more than the protocol-specified dose. The effects of any potential overdose with BE1116 have not been studied. In case of overdose, the subject should be closely monitored, and supportive treatment should be administered, as needed.

See [Section 9.6.5](#) for overdose reporting requirements.

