^a Vital signs obtained as part of standard of care will be recorded at Screening prior to infusion, except as described. These include supine systolic and diastolic blood pressure (mmHg), pulse rate (bpm), respiratory rate (breaths per min), pulse oximetry (%), and body temperature (°C). Body weight (kg) will be estimated or measured on arrival at the hospital and used to define the dose of IP. If estimated, weight may also be subsequently measured. Height (cm) will be measured or taken from medical history.

^b To be performed at Screening prior to IP infusion, except as indicated.

^c To be recorded when feasible.

^d To be recorded from the subject's medical records (if available). The initial hematology, coagulation, and blood gas measurements only will be recorded in the eCRF from medical records. Initial = the first value obtained after arrival at the hospital prior to IP infusion.

^e To be recorded at any time from Screening through the In-hospital Follow-up Period from the subject's medical records.

^f To be recorded at any time during the In-hospital Follow-up Period from the subject's medical records.

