9.6.5 Overdose

Any overdose that is associated with an AESI or SAE will be recorded on an AE / SAE eCRF form (see also [Section 9.6.3](#)).

Details of overdose of IP (defined in [Section 5.1.3.4](#)) must be recorded in the study treatment administration eCRF.

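### SAP 11.1 uses 'overdose' for weight-band disagreement, contrary to the protocol's definition, and has no dedicated row for protocol-defined overdoses or for most partial doses

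*SAP*

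**What the plan says.** Protocol 3.2 assigns 2000 IU below 75 kg and 3000 IU from 75 kg upward, "based on the estimated or measured weight of the subject documented on arrival at the hospital". The footnote to the table in Protocol 8.1.1 agrees: "Body weight (kg) will be estimated or measured on arrival at the hospital and used to define the dose of IP". It adds that an estimated weight may be measured later. Protocol 3.3.2 accepts either kind of weight for dosing.

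Protocol 5.1.3.4 gives the definition: "Overdose of BE1116 is defined as the infusion of more than the protocol-specified dose". Protocol 9.6.5 says that overdose details "must be recorded in the study treatment administration eCRF". Protocol 5.1.1 describes each kit as "containing 3 vials of BE1116 (or placebo), 3 vials of sterile water for injection", so a kit opened for a two-vial subject holds a third vial. Protocol 5.1.3.2 states "A partial dose of IP may be administered", and its examples are product or user error, patient care issues and damaged vials.

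SAP 10.6 drops a compliance evaluation and says: "Issues with the administration of the single dose will instead be included in the exposure summary described in Section 11.1". SAP 11.1 then summarises, in the Safety Population:
- dose level (2000 or 3000 IU)
- infusion duration
- infusion rate
- interrupted infusions by reason
- infusions stopped because of an adverse event
- "Number and percentage of subjects whose dose level would be different if measured weight instead of estimated weight has been used (overdose and underdose"

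All administrations are also listed.

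**The concern.** Overdose is a defined safety term in the protocol, with its own eCRF recording requirement, and limiting its risk is one stated reason for the 50 kg minimum weight (Protocol 4.1.1). A reader of the study report who sees an overdose count in the exposure table will take it in the protocol's sense. Under SAP 11.1 that count would be something else: how often a weight estimate fell on the wrong side of 75 kg.

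The second issue is coverage. The mITT and Safety Populations both include subjects who received only part of a dose. If the section assigned to administration issues does not tabulate partial doses, the summary does not show by arm how many treated subjects received the intended amount.

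**Working it through.** **1. The two definitions side by side.** Let D be the amount infused, A the dose assigned from the arrival weight used for dosing, and M the dose that a later measured weight would have assigned.
- Protocol overdose: D > A.
- SAP 11.1 'overdose': A > M.

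D does not enter the SAP condition, and M does not enter the protocol condition. Two constructed subjects show both failures:

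| Subject | Estimated on arrival | Measured later | Infused | Protocol 5.1.3.4 | SAP 11.1 row |
|---|---|---|---|---|---|
| 1 | 76 kg | 74 kg | 3000 IU | As assigned | Overdose |
| 2 | 55 kg | 55 kg | 3000 IU (all three vials) | Overdose | Not counted |

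Per kilogram, subject 1 receives 3000/74 = 40.5 IU/kg and subject 2 receives 3000/55 = 54.5 IU/kg. The row flags the smaller exposure and passes the larger.

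**2. Possible size of the mislabelling.** The documents contain no weight data, so this rests on assumptions: true weight Normal with SD 16 kg and mean 75, 82 or 90 kg; unbiased estimation error with SD 5, 10 or 15 kg; both weights at least 50 kg; cut at 75 kg. Every subject is dosed exactly as the protocol assigns on estimated weight, so the true overdose rate is 0%. Simulated percentages labelled overdose / underdose by the SAP row:

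| Mean weight | Error SD 5 kg | Error SD 10 kg | Error SD 15 kg |
|---|---|---|---|
| 75 kg | 5.3 / 5.2 | 9.9 / 9.9 | 13.9 / 13.3 |
| 82 kg | 4.2 / 4.9 | 7.4 / 9.9 | 9.8 / 13.9 |
| 90 kg | 2.7 / 3.8 | 4.4 / 8.3 | 5.5 / 12.5 |

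The ranges are 2.7% to 13.9% overdose and 3.8% to 13.9% underdose. The proper denominator is subjects with both weights, which the SAP row does not state.

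**3. Early stops and partial doses in SAP 11.1.** Stops are counted through an adverse event whose action is Drug Withdrawn. Only SAEs and AESIs are recorded (Protocol 9.6.1, SAP 11.2), so an infusion ended for a nonserious reaction outside the AESI list leaves no record for that row. Neither need one ended for user error, a damaged vial or confirmed pregnancy (the example in Protocol 4.3.1). The interruption row is not a clear home for these cases. The duration formula subtracts interruptions as pauses within an infusion, and SAP 11.2 treats dose interruption and discontinuation as separate categories. A one-vial dose (1000 IU) fits neither dose-level category if the category means delivered dose.

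**4. Infusion rate.** SAP 11.1 converts 1000 IU to 40 mL. Reproducing the protocol's volumes: 2000/1000 × 40 = 80 mL and 3000/1000 × 40 = 120 mL, both as in Protocol 5.1.1. The conversion is correct, but the SAP does not say whether the dose converted is planned or delivered. If planned, the rate for a partial dose is overstated by planned/delivered vials: 3/2 = 1.5, 2/1 = 2 or 3/1 = 3. For example, 120 mL planned but stopped at 60 mL after 7.5 minutes gives 120/7.5 = 16 mL/min instead of 60/7.5 = 8 mL/min. If delivered, there is no error.

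**The case against.** The strongest reply is that the row says in words what it counts, so the count is correct and the parenthesis only gives the direction of the discrepancy. SAP 9.3 reports the same disagreement between weight categories without the word overdose. This shows that the number is not miscalculated. It does not make the label agree with Protocol 5.1.3.4.

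A reader might infer that overdoses and partial doses are never counted anywhere. The documents do not support that. SAP 9.2 summarises by arm the deviations that require exclusion from the Per-protocol Population, including incorrect dosage. SAP 9.1 summarises treatment status by arm, Protocol 10.3.1.1 lists reasons for discontinuing the product, and SAP 11.1 lists all administrations. What remains is narrower. Incorrect dosage is not split into over- and under-dosing and is reported for the ITT and mITT Populations rather than the Safety Population. Partial doses are permitted, so they need not be deviations at all.

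A reader might also infer that the exposure figures will be wrong. That is not shown: dose level and rate go wrong only if planned amounts are used for partial doses, and the SAP is silent on this. SAP 10.1.4 uses the planned dosing group, but only for the subgroup analysis.

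Nor is 50 IU/kg the protocol's overdose test. Protocol 3.3.2 cites it as the top of the approved range for warfarin reversal, so the per-kilogram figures above illustrate exposure and do not classify cases.

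**Conclusion.** The conflict in terms is real. The 'overdose' row in SAP 11.1 can include compliant doses and omit protocol-defined overdoses, and the two documents must be reconciled. SAP 11.1 also lacks a dedicated row for partial doses and for early stops without a recorded adverse event, despite the referral from SAP 10.6. Infusion rate is an ambiguity, not a demonstrated error.

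The size in this trial is unknown. The 2.7% to 13.9% range for compliant doses labelled overdose depends entirely on the assumed weights and estimation errors. The documents give no basis for estimating how often true overdoses or partial doses occurred.

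This is a minor point about descriptive safety reporting. It does not affect the primary analysis, and it implies no view on the dose or on any clinical rule.

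**What to change.** In SAP 11.1:
1. Relabel the row as dose band differing between estimated and measured weight, use subjects with both weights as the denominator, and drop the words overdose and underdose.
2. Add by-arm counts of subjects infused with more than their protocol-assigned dose, taken from the study treatment administration eCRF, and of subjects with complete and partial doses, with the reason where recorded.
3. Compute infusion rate from delivered volume, or restrict it to complete infusions.

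The cost is a change of SAP wording and a few table rows. The protocol already sends overdose details, infusion start and stop times and interruptions to the eCRF, the timing details only where available (Protocol 5.1.3.1). The eCRF itself is not among the documents, so whether it holds the delivered volume for every partial dose should be confirmed. If it does not, restricting the rate to complete infusions needs no new data.
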